4.2 Restriction of Study to Fresno County, California

All MEs for the aerosol application monitoring study will be conducted in rooms inside vacant buildings (or inside non-occupied rooms within non-vacant buildings) in Fresno County, CA. This particular geographic area was selected given its proximity to the analytical laboratory. Fresno County also contains a moderately large metropolitan area and offers a population of over 500,000 persons. Consequently, there is a substantial janitorial population whose members are potentially acceptable for monitoring activities.

The use of a single geographic area is based on the premise that the type and variety of indoor janitorial aerosol application tasks being performed throughout one geographical area will not differ substantially from a similar array of tasks being performed at sites in another geographical area. That is, the variation in exposure associated with aerosol application inside of buildings throughout Fresno County, CA would not be expected to differ substantially if another metropolitan area was used or multiple cities over the country were spanned. This premise is supported by the Popendorf et al. (1992) antimicrobial exposure monitoring study which concluded that variability in dermal and inhalation exposures across workers was primarily influenced by the application method and by implication, each individual worker's implementation of that application method (i.e., their work practices and behavior), rather than the location or setting in which the application method is performed. This implies that monitoring multiple subjects and capturing diversity in indoor aerosol application conditions that might influence behavior is more important than geographic diversity.

Geographic differences in exposure that have been observed in some agricultural cohorts are not expected for aerosol applications. For example, in harvesters, climatic conditions that influence the degree of dustiness, the rate of dissipation of foliar pesticide residues, or the amount of perspiration may influence exposure. Those differences cannot really be considered regional, but rather environmental. In the case of janitorial services conducted indoors, the environmental conditions are constrained by heating, ventilating and air conditioning systems that control dustiness, temperature, humidity and airflow. Therefore, these conditions are expected to be similar throughout the country.

Limited standardization of janitorial practices is another factor that is expected to lessen the importance of geographic area. The janitorial business is supported by organizations (e.g., International Sanitary Supply Association; www.issa.com) and companies (e.g., JohnsonDiversey; www.johnsondiversey.com; JohnsonDiversey offers a "Power Tools" training series) that supply

training and guidance on issues such as duration of a particular job function, the types of supplies that are required and how to use equipment and supplies most efficiently. This helps to insure that janitorial work tasks are conducted somewhat uniformly across the country. By examining the documentation supporting training and use of janitorial supplies, the AEATF II found no evidence of regional work differences.

Lastly, there is increased efficiency, convenience, and cost savings associated with the use of a single location near the analytical laboratory. The use of buildings located over multiple cities would be especially costly. The cost of selecting both buildings and subjects would increase at least in proportion to the number of geographic locations due to field team logistics and resources required. For the reasons outlined above, there would appear to be little benefit from such an increase in cost.

5. Construction of Monitoring Events

As noted above a combination of random sampling and diversity selection is being used by the AEATF II to obtain N monitoring events (MEs) for the aerosol application study. In the AEATF II approach, instances of possible handler-day conditions under the scenario are synthetically constructed and handler-day exposures measured. Although application conditions are synthetic, actual applicators will have been randomly sampled from among professional applicator volunteers recruited from janitorial services located in Fresno County California. Each of N professional applicators will be randomly assigned to one of the N synthetic applicator-days. Each combination of applicator and set of synthetic application-day conditions comprises a single monitoring event (ME).

The synthetic application-day conditions are either purposively or randomly chosen in such a manner that the MEs capture diversity likely in the aerosol application scenario. The approach used by the AEATF II achieves diversity by:

- 1. Using multiple sites (i.e., facilities/dates) within the study area (Fresno Co., CA) rather than conducting all monitoring at a single site;
- 2. Varying the levels of potential AI contact among MEs within each site.
- 3. Using a different subject for every ME.

Diversifying these three 'meta-characteristics' (site, AI contact level, and subject) indirectly varies many known and unknown application-conditions. Additional diversification by varying minor ME application-conditions (e.g., different configurations of aerosol surfaces) may also be added but is not a formal part of the design.

The resulting set N MEs provides a diverse set of applicator-days that mimic the diversity likely within the actual aerosol application scenario. The AEATF II has determined, in consultation with the U.S. EPA, Health Canada, and California EPA, that this combination of random sampling and diversity selection is appropriate considering the regulatory purpose of the data and feasibility. As described below, a diversity selection approach is one that can be purposive or can be coupled with random choice elements when feasible to reduce intentional selection bias.

The AEATF II Governing Document (2008) describes diversity selection more generally in the context of the AEATF II antimicrobial exposure assessment program.

5.1 Random Sample of Professional Applicators

The most important single meta-characteristic that is formally varied when constructing MEs is the applicator. These are professional workers with experience in performing aerosol applications, who are available and consent to perform these tasks under the synthetic application-day conditions of the study. Although these applicators will be a random sample from an existing population of workers, they can be equally viewed as just another component of the synthetic ME being constructed to predict a single instance of a future day's exposure to an arbitrary antimicrobial pesticide. Each selected worker provides his/her unique set of behaviors to the aerosol application task. A random sample of applicator-days could, in theory, contain two or more days with the same worker. However, the random sampling method used for this study permits only one monitoring event per worker in order to capture a larger diversity of application behaviors.

The applicators will all be professional janitorial workers in the Fresno County, CA metropolitan area. Flyers and/or advertisements soliciting subjects will be posted at all cooperating janitorial service providers in the area and in selected local print media (all materials will have been reviewed and approved for use by the IRB). Callers responding to flyers and/or media advertisements who are interested in participating in the study may be scheduled for Informed Consent meetings at the volunteer's convenience. It is not necessary to wait until the recruiting period is closed before enrollments begin. These individuals will then be contacted and screened, individuals who meet the study requirements will be recruited until the required number of applicators is obtained. As a precaution, more applicators are selected than are expected to be needed. Individuals who are enrolled to participate in the study will then be randomly ordered and assigned a subject identification sequence number (SISN). This random sample of workers is then allocated to MEs by SISN.

The recruitment process will terminate when sufficient subjects have been recruited for the study, i.e., have agreed to participate and signed the ICFs. If fewer than the required number of subjects has been recruited during the open recruitment period, the enrollment period will be extended in 7 days increments, until at least the minimum number of subjects and alternates have been enrolled into the study.

This process results in a simple random sample of qualifying subjects from the volunteer pool. Note, however, that this is not technically the same as a random sample from the existing population of professional janitorial workers. By definition, volunteers are self-selected and could, in theory, have different characteristics than non-volunteers. Such fine distinctions have little relevance in this case, however, because this is not an observational study of existing applicator-days. Because workers are randomly assigned to synthetic application-day conditions, the resulting MEs are still considered synthetic applicator-days. Thus, any type of random sampling of just one ME component (e.g., applicator in this case) provides no statistical advantage other than reduction of selection bias.

5.2Selection of Monitoring Sites

Monitoring will always be conducted within vacant lodging facility buildings or vacant areas and rooms within otherwise occupied buildings. The purpose in conducting these studies in vacant or unoccupied areas in buildings/areas is to be free from personal interferences with non-subjects and the potential contamination from other sources of a commonly-used active ingredient (i.e., ADBAC). It also makes it easier to design monitoring events that focus on aerosol application only as opposed to the broad range of janitorial activities a subject might engage in that could also involve the active ingredient. Using vacant or unoccupied areas in buildings also offers greater control of the scheduling of monitoring events.

Each combination of facility (building or building complex) and monitoring period (i.e., dates) is termed a 'site'. Diversity is induced by requiring that the N monitoring events occur at N_C different sites over the Fresno County metropolitan area. As noted above, environmental conditions (e.g., temperature, humidity, air exchange rates) may be similar between facilities and at different times. On the other hand, buildings and dates might still be surrogates for other confounding factors that could cause systematic differences in exposure. Conceivable confounding factors might be architectural differences in room size, construction materials and configuration, and dirtiness or organic loading levels on surfaces to be cleaned. Temporal separation of sites tends to average out subtle 'study effect' correlations that can result when the same research personnel, equipment, and area-wide environmental conditions are involved.

Obviously, between-site diversity is maximized if every ME for a scenario occurs at a different site (i.e., $N_C=N$). However, there are practical efficiencies to be gained by conducting multiple MEs (i.e., N_M) per site. Consequently the aerosol study achieves a balance by using multiple sites with multiple MEs per site. Any correlation resulting from having multiple MEs/site can be overcome, at least partially, by also increasing within-site diversity. Thus, facilities are preferred if they provide diverse indoor room and area configurations, e.g., individual offices, bathrooms, kitchen areas, dining areas.

For the AEATF II Monitoring Program, the term cluster is defined as the set of MEs for a scenario associated with the same building (or building complex) and span of days during which exposure monitoring occurs. In contrast, the term site refers to the physical facility and temporal monitoring period considered together as a unit (the temporal aspect of a site is not always emphasized but is important nevertheless). A total of N_C sites are required for the aerosol scenario. Each site will be used for a single cluster of N_M aerosol application MEs. The set of different sites should posses the following general design characteristics:

- 1. Each site must be located in a different facility (i.e., building or building complex).
- 2. The configuration of rooms actually used for MEs at the different sites should differ in ways that might influence exposure.

For purposes of the aerosol application study, the available space in each facility must also be large enough and have bathrooms and/or food preparation areas (e.g., kitchens or 'kitchenettes')

that provide relevant and adequate surface areas for aerosol treatment. Commercial lodging facilities (e.g., hotels, motels with kitchenettes or full kitchen, and/or if needed, small apartments) are buildings that are most likely to provide an adequate amount of relevant aerosol application surface area for the monitoring events, e.g., bathroom sinks and fixtures, toilets and fixtures, bathtubs and fixtures, shower stalls and fixtures, bathroom counter tops, kitchen sinks and fixtures, kitchen countertops, and trash cans. While other building types, such as offices (e.g., medical suites) and meeting locations (e.g., universities) represent locations where disinfecting aerosols may be applied, and provide diversity in architecture and floor plan, these categories are less likely to provide the number of separate rooms and surface areas needed for the range of amount of aerosol to be sprayed.

A random sampling approach will be used to select N_C acceptable facilities. First, a list of all properties that meet the following criteria will be compiled:

- The property is commercially advertised on YellowPages.com or similar listings under "hotel, or motel" in "Fresno County, California," and;
- The property is at least partially within the boundaries of Fresno County, California; and

This list of commercial lodging facilities will then be randomized. Next, these properties will be investigated in (random) order until N_C qualifying facilities have been found. To qualify, the properties must meet the following general criteria:

- The facility management is willing to cooperate in the study and provide the necessary number of units with bathrooms and/or food preparation areas (FPAs).
- The configuration of available and ME-suitable rooms provides acceptable diversity of application surfaces (e.g., horizontal and vertical surfaces, kitchens, bathrooms, sinks, countertops, toilets).
- There is a functional HVAC system
- Electric service is on or available for a short period (i.e., less than 32 days).
- The property does not require specialized cleaning or maintenance prior to use.

In addition to these criteria, an acceptable facility must also fall into one of N_C different building/room categories (see Section 6.5). To insure diversity among the selected sites, only a single facility will be selected from each category. Properties will be investigated (in random order) until the first N_C acceptable facilities are found.

This procedure results in a (stratified) random sample of N_C acceptable and diverse facilities from the population of all such qualified facilities in Fresno County, California. Monitoring activities are then scheduled purposively for each facility.

5.3Varying Amount of Product Applied

Another key diversity meta-parameter used to construct synthetic application-day conditions is the amount of active ingredient handled (AaiH). All MEs in the study will apply the same active ingredient at the same concentration using a different number of 19-oz (538 g) aerosol cans. Consequently, AaiH will be directly proportional to of the total amount of product (i.e., number of cans) sprayed during the monitoring period. To properly diversify the amount of product sprayed, some reasonable estimate for the expected range of this meta-parameter among professional applicators is needed. Data on the total amount of product applied are unavailable. Consequently, the expected range must be inferred indirectly from existing data on components of total workday product use.

Table 2 summarizes information on the average amount of formulated aerosol or trigger spray product applied to various surfaces in bathrooms and kitchens during observed cleaning events. These data were obtained from an observational study of actual product use by consumers (Aklam et al., 2006).

Table 2: The amount of product formulation (aerosol and trigger sprays) applied (g) for bathroom and kitchen surfaces.

Location	Type of Surface	N	Mean Amount Sprayed, g
	Counter	12	10.16
	Sink	6	9.04
Bathroom	Toilet	15	11.91
Bumoom	Tub/Shower/Shower Door	15	93.31
	Wastebasket	3	3.67
	Counter	13	41.50
Kitchen	Sink	9	22.14
	Wastebasket	4	34.95

Each row in Table 2 only characterizes cleaning events for individual surface types, not the entire room. The mean amount of product applied if an entire room were treated can be approximated by assuming that a bathroom or a kitchen contains one surface of each surface type listed in Table 2. The resulting two room totals are shown in Table 3 along with the amount averaged over both room types. This overall average of 113 grams/room represents the mean total amount of product used in a 'generic' or 'typical' room treated on a given workday.

Table 3: The estimated average total amount of product formulation applied (g) when treating either the entire bathroom or the entire kitchen.

Room Type	Mean Amount of Product Used (g/room)
Bathroom	128.1
Kitchen	99.59
Generic Room ¹	113.3

¹ A 'typical' average amount of product used per room per day based on bathrooms and kitchens.

Obviously, 113 grams represents only the mean amount of product applied per room by a residential consumer. The actual amount will vary from room to room, from day to day, and from person to person. However, this amount is not expected to vary independently. There will certainly be some degree of correlation for all rooms cleaned by the same individual. More importantly a negative correlation is expected to exist between the total number of rooms per workday and the amount of product used per room. That is, when a larger number of rooms are treated, there could be a tendency to spend less time, and apply less product, per room.

Logically, on days when antimicrobials are used, at least one room will be treated. In this case 113 grams of product would be used on average. This translates to 21% of the 19 oz (538 g) canister that will be used for this study. Given the negative correlation between number of rooms/day and amount/room, this lower bound should probably be larger than the generic room average. (i.e., more than the 'average' amount of product might be sprayed on surfaces when only a single room is cleaned). In addition, for the AEATF II aerosol study, the analytical method LOQ sets a practical lower limit on the amount of product that should be used for an ME. Obviously it is desirable to obtain actual measurements, rather than non-detects, beneath normal work clothing. For this scenario, it is felt that a practical lower bound of one canister (i.e., 538 grams) per ME will achieve detectable levels of active ingredients on dosimetry matrices.

Information about the upper limit on number of rooms/day is based completely on inferences about the professional housekeeping population. Aerosol products used by professionals are in smaller, specialty business venues, such as medical offices and specialty hotels. Thus, while consumers may treat only a single kitchen and one or two bathrooms on a single day, this number in institutional settings such as hospitals is expected to be much larger. According to JohnsonDiversey Inc. (personal communication with AEATF II, September 19, 2008), information from multiple sources¹ indicate that a single individual at a hospital would typically

¹ JohnsonDiversey's expert opinion was based in part on information from the following sources: 1) the American Hospital Association (http://www.aha.org/aha_app/index.jsp), the American Society for Health Care Environmental Services (http://www.ashes.org/ashes_app/index.jsp), and the U.S. EPA's Environmental Best Practices for Health Care Facilities (JCAHO Environment of Care Standards 1.3,2.3,4.0, November 2005).

clean from 15 to 20 hospital patient rooms per day. However, aerosol use is more likely at medical and dental offices and specialty lodging facilities than in hospitals. In these settings JohnsonDiversey Inc. feels that the typical range would extend below 15 rooms per day. Consequently, 20 rooms/day would appear to be a reasonable upper bound for professional aerosol applicators.

As noted above, when such a large number of rooms are cleaned per day, it is very likely that the mean amount of product applied per room will be less than the 'overall average' of 113 grams. However, using 20 rooms/day and 113 grams of product per room should still provide a conservative upper bound for total product applied per day by professional cleaners. This approximation gives a maximum of 2,260 grams of product (113 g/room x 20 rooms/day), or about 4.2 19-oz canisters (2,260 g / 538 g per canister), per day.

Thus, these results suggest that reasonable diversity in AaiH among MEs could be obtained by varying the number of 19-oz canisters applied between 1 and 4. This will be accomplished by dividing this range into N_M intervals, or strata, of amount of product (i.e., number of canisters) sprayed (see Section 6.5). Each of the N_M MEs at a site will be assigned to one of these product use intervals.

5.4Potential Sources of ME Bias

As noted above, a practical study goal is that the set of aerosol application MEs represents a diversity of potential applicator-day conditions that might impact exposure. To the extent this is achieved, the set of MEs will tend to exhibit greater variation in log-exposure than would an actual population of all possible applicator-days. Because applicator-day exposures are expected to be distributed lognormally, greater variation of log-exposure implies greater positive skewness of non-transformed exposure. Consequently, statistics that are sensitive to positive skewness (e.g., arithmetic mean and upper percentiles) might be biased upwards.

It is also important to recognize that some degree of potential overestimation bias is inherent in any study if the exposures measured on the inner dosimeters from MEs are less than limit of quantitation (LOQ). This is more likely to occur when the amount of product applied is smaller, although AEATF is making every effort to obtain measurable exposures for all MEs.

Another potential source of inherent potential overestimation bias in the study design described in this document and the associated protocol is reusing the same rooms for multiple applicators. The residue remaining from a prior day's use might represent a significant source of dermal contamination for subsequent users.

Other potential sources of potential overestimation bias result from characterizing all aerosol exposure from situations having higher-than-average exposure potential such as:

- spraying in an enclosed space (e.g., shower enclosure),
- spraying above and below the chest height,
- spraying near air exhaust vents, or

• walking into spray mist sprayed overhead.

For most regulatory users of these data, however, potential overestimation of exposure will likely be of little concern because it would still be inherently protective of workers. The AEATF does not foresee significant sources of underestimation bias for exposure estimates derived from data resulting from the proposed study.

6. Sample Size Determination

For the most part, sample sizes can only be determined using statistical theory alone when either

- 1. There is assumed random sampling from a population and the goal is to estimate some characteristic of that population; or
- 2. There is assumed randomization of experimental units to treatments and the goal is only to compare or contrast treatments in some manner; or
- 3. It is assumed that all non-random influences can be mathematically 'removed' in some fashion through modeling and any remaining deviations from the model are 'naturally' random (although such natural residual randomness may take a complicated form).

Only in these general situations can statistical theory predict how increasing sample size decreases estimation error. In other data-collecting situations, sample size must be determined using one of the three 'random' situations above as a reference model. The random reference model is constructed so that it reflects important aspects of the actual situation. The sample size that is appropriate for the reference model is then used for the actual study design. The use of a random reference model is not, however, a claim that the pure situation described by the reference model actually occurs.

This random reference model approach is used to determine sample sizes for the aerosol application scenario. The aerosol application study will utilize a combination of random sampling, randomization, and diversity selection methods. While this methodology contains some elements of all three pure situations above, none apply completely. The ultimate goal of this study is to construct synthetic MEs that can be used to characterize the diversity of future daily exposures to antimicrobials through aerosol application. Hence, the study objectives are more closely aligned with the random sampling situation (1) above. As a result, a reference model for random sampling will be used for the determination of sample size.

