An antimicrobial handling scenario is a set of related tasks, pesticide formulations, equipment, engineering controls, and worker and/or consumer practices. For the purposes of the AEATF II antimicrobial exposure assessment Program, the aerosol application scenario is defined as the hand-held pressurized aerosol-based application of a label-specified end-use formulation containing an antimicrobial chemical. This includes the task of actual aerosol spraying for purposes of air and surface odor elimination, sanitizing, or disinfecting. The aerosol application scenario involves application according to typical practices, e.g., spraying surfaces from a distance of approximately 6-10 inches in a manner to apply enough formulation to provide an adequate amount for cleaning. Hard surface applications are typically sprayed until visibly "thoroughly" wet per label direction. No wiping will be conducted as part of this application scenario. Surface applications are typically made in smooth, sweeping, overlapping patterns. Examples of "representative" spray application techniques that this scenario is expected to capture include horizontal spraying moving upward and downward from the starting point to hard surfaces such as laminate, tile, porcelain, glass, and metal). The ready-to-use (i.e., no mixing or loading procedures are involved) pressurized aerosol represents a common application method in residential (consumer) settings, and is also used in institutional settings, as an alternative to "dilutable" products, such as an end-use solution filled into a trigger sprayer. The aerosol application scenario is being used to address potential exposures to hand-held spray products in general, including surface disinfecting sprays, air sanitizers, and foaming aerosols. The pressurized disinfecting aerosol spray was selected to represent this group of spray products because it is a commonly used product type, the application process (spray nozzle actuation) is similar across all aerosol product types, and the surface application rates, normalized to mass of

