The scenario design in Section 6.4 indicated that NC=3 clusters are required. As discussed in Section 5.2 each of these three clusters of MEs should be conducted at a monitoring site that can be generally described as a qualifying commercial lodging facility (i.e., hotel, motel with kitchenette or full kitchen). MEs will be conducted in available bathrooms and, if present, food preparation areas within the facility. A food preparation area (or FPA) is defined as a room containing a stove/oven, refrigerator, and food preparation sink.

A simple random sample of qualifying facilities could be selected. However, this might result in two or more monitoring sites with similar configurations of ME-appropriate rooms. Although valid, greater diversity among monitoring sites can be obtained if each of the three clusters is conducted in a somewhat different room configuration. Consequently, for the aerosol application study the AEATF II will consider only the following three building/room configuration categories:

- A. Hotels/motels with 20 or more available units containing full kitchens
- B. Hotels/motels with 20 or more available units containing kitchenettes
- C. Hotels/motels with 20 or more bathroom-only units.

These three categories were chosen because they vary with respect to bathroom and FPA (i.e., kitchen or 'kitchenette') configurations which might be expected to impact exposure potential differently. Although other, equally acceptable, classifications could be proposed, this one is considered both intuitive and logistically practical.

As described in Section 5.2 above, one facility will be randomly selected from each category. It is important to emphasize that this study is not concerned with testing whether average exposure differences exist between the three different configuration categories. Nor would it be especially relevant if true exposure differences actually do not exist, on the average, between these categories. Rather, the purpose of the patterned randomization is simply to reduce the likelihood that the three selected monitoring sites will be too similar by chance.

The scenario design also requires $N_M=6$ MEs within each cluster. As noted in Section 5.3, each of these MEs will require an amount of product in the range of 1 to 4 19oz cans. Thus, a reasonable approach is to require that the six MEs have applicators apply product amounts somewhere within the following six ranges:

A. 1 to 1.5 cans

B. 1.5 to 2 cans

C. 2 to 2.5 cans

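### Rooms are reused and residue is conceded, but no run order is set for the six product amounts at a site, so dermal carry-over can line up with amount handled

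*Combined protocol and SAP*

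**What the plan says.** - **Reuse and residue.** Section 5.4 says one inherent source of overestimation "is reusing the same rooms for multiple applicators", in this document and in the associated protocol. It adds: "The residue remaining from a prior day's use might represent a significant source of dermal contamination for subsequent users". Neither the number of reuses nor the size of the carry-over is given.
- **Scheduling.** Section 5.2 ends its account of facility selection with: "Monitoring activities are then scheduled purposively for each facility".
- **Randomisation.** Section 5.1 puts enrolled workers in random order and allocates them to monitoring events (MEs) by sequence number. Section 6.5 assigns the 18 applicators at random to the 18 combinations of site category and product interval. Neither section fixes the calendar order of the six intervals at a site.
- **Rooms and amounts.** Section 6.5 sets minimum sizes, such as "Hotels/motels with 20 or more bathroom-only units" and "Hotels/motels with 20 or more available units containing full kitchens"; the kitchenette category has the same minimum. At each site, "each of these MEs will require an amount of product in the range of 1 to 4 19oz cans", in six half-can intervals.
- **Sponsor's position on the bias.** Section 5.4 regards overestimation as of little concern to most regulatory users because it protects workers.

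**The concern.** Randomising applicators to cells prevents confounding by applicator. It does not stop residue from building up in step with product amount. If a site runs its small amounts first, its large-amount MEs work in the most heavily sprayed rooms; if it runs large amounts first, the reverse happens. In either case part of the measured dermal exposure comes from other people's product, and that part varies with the amount handled.

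This differs from the uniform upward shift that Section 5.4 accepts as protective. Section 4 names proportionality of exposure to amount handled as one of two principles that let these data be generalised. Section 6.5 leaves users free to analyse exposure by volume. A user who did so could not separate a true departure from proportionality from an effect of run order. If prior room use is not recorded in the field, it may be impossible to reconstruct.

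**Working it through.** **1. Reproduce the plan's per-room figure.** The bathroom surfaces in Table 2 sum to 10.16 + 9.04 + 11.91 + 93.31 + 3.67 = 128.09 g. The kitchen surfaces sum to 41.50 + 22.14 + 34.95 = 98.59 g. Their average is 113.3 g, as Table 3 states. (Table 3 prints the kitchen total as 99.59 g; the 113.3 g average agrees with 98.59 g, and nothing here depends on the difference.) The plan gives no reuse figure to reproduce.

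**2. Product per site.** MEs are run "using a different number of 19-oz (538 g) aerosol cans". The interval midpoints are 1.25, 1.75, 2.25, 2.75, 3.25 and 3.75 cans, which sum to 15 (range 13.5 to 16.5). 15 × 538 g = 8,070 g.

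**3. Passes per unit** = grams per site / (grams per unit × units).

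| Site type | g per unit | 20 units | 40 units | Units for no reuse |
|---|---|---|---|---|
| Bathroom only | 128.1 | 8,070 / 2,562 = 3.15 (2.8 to 3.5) | 1.6 | about 63 |
| Bathroom plus kitchen | 226.7 | 8,070 / 4,534 = 1.78 (1.6 to 2.0) | 0.9 | about 36 |

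These are total passes, so repeat use after the first pass is about 2.1 and 0.8 at 20 units.

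**4. Illustration of alignment.** Assumptions, none of them from the documents: 20 units, whole rooms used in rotation, and each prior spray of a room adding 10% to dermal exposure. The multiplier for an ME is 1 + 0.10 × mean prior sprays of its rooms.

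- *Bathroom only, ascending.* The six MEs need 5, 7, 9, 12, 14 and 16 rooms. Mean prior sprays are 0, 0, 0.11, 1.00, 1.50 and 2.19, so the multipliers are 1.00, 1.00, 1.01, 1.10, 1.15 and 1.22.
- *Bathroom plus kitchen, ascending.* The MEs need 3, 4, 5, 7, 8 and 9 units. Mean prior sprays are 0, 0, 0, 0, 0.88 and 1.00, so the multipliers are 1.00 for the first four MEs, then 1.09 and 1.10.

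The table gives the least-squares slope of log multiplier on log amount (zero under proportionality) and the mean inflation. Random order is the average over all 720 orders.

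| Order | Bathroom only: slope | Mean inflation | Kitchen: slope | Mean inflation |
|---|---|---|---|---|
| Ascending | +0.18 | 8% | +0.09 | 3% |
| Descending | -0.20 | 14% | -0.10 | 6% |
| Random | about 0 | 11% | about 0 | 4% |

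A variant calculation puts the random-order average slope at +0.04 and +0.02, still near zero. At 40 units the kitchen site has no reuse and so no spurious slope; the bathroom-only ascending slope falls to about +0.07.

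**5. Against sampling error.** With 18 MEs and the plan's GSD of 2.9, the standard error of the pooled slope is ln(2.9) × √(1 − ICC) / √Sxx, where Sxx = 3 × Σ(ln midpoint − mean)² = 2.51. This gives 0.67 at ICC 0 and 0.56 at ICC 0.3. If all three sites ran ascending, the average spurious slope would be (0.18 + 0.09 + 0.09) / 3 = 0.12, about a fifth of that standard error.

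**6. What randomising leaves.** With six MEs, the correlation between run position and amount has mean 0 and SD 1/√5 = 0.45 at one site. In 214 of the 720 orders (30%) it is 0.5 or more in absolute value.

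**The case against.** The strongest reply has four parts.

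- **The scheduling sentence may concern only when each facility is visited.** It closes the facility-selection procedure, and a site is defined as a facility plus its dates. A reader might infer that amounts are purposively ordered within a site. The text does not say so; the order is unstated. MEs might even be run in the random sequence-number order, which is not stated either way. The gap is therefore a missing rule, not a bad one.
- **Room handling may be covered in the associated protocol.** That protocol is not in this text. A reader might infer that rooms are never cleaned between MEs from Section 2: "No wiping will be conducted as part of this application scenario". That sentence defines the applicator's task; cleaning between MEs is not addressed. However, Section 5.4 attributes the reuse and residue problem to the associated protocol as well, so the concession stands.
- **The bias is disclosed and volume comparison was not a sizing objective.** Both are true. Disclosure covers direction on average, though, not alignment with amount.
- **Randomising does not protect the benchmark estimands.** This also stands. Mean inflation is much the same under random order, and heavier reuse at the bathroom-only site remains.

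The reply therefore limits the size and wording of the point without removing it.

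**Conclusion.** The point holds as a low-cost design improvement. Reuse and possibly significant dermal residue are conceded, reuse follows from the plan's own figures at minimum-size sites, and no stated rule stops run order from following product amount.

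The reuse counts of about 3.2 and 1.8 passes rest on the 20-unit minimum and on consumer per-room amounts; larger sites reuse less. The slopes of about +0.18 and +0.09 rest on an assumed 10% carry-over and a fully ascending order. A reader might infer a larger distortion, such as inflation of 1.24 to 1.71 times at the largest amount and a slope of +0.19 to +0.48. Those figures combine an assumed 10 to 30% carry-over with the minimum unit count, the worst of the three site types and one order in 720, so they do not describe the study as a whole. Nor should the point be extended to inhalation exposure: the plan's concession names dermal contamination only.

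The shift in the mean at 10% carry-over, about 3 to 14% depending on site type and order, is small against the 3-fold accuracy benchmark. The sample size of 18 is not affected. What is at stake is whether the data can later support a check of proportionality.

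**What to change.** - State the run order of the six product-use intervals at each site. Randomise it separately by site, or choose three orders balanced so that each interval has a similar average run position across the sites. Balance is preferable because six MEs per site leave appreciable chance imbalance.
- Use unsprayed rooms first and spread any reuse evenly over the six intervals.
- Record run order and the number of prior sprays of each room for every ME, and state whether rooms are cleaned between MEs.
- Report one sensitivity analysis of log normalised dermal exposure with mean prior sprays per room as a covariate. With 18 MEs it will be imprecise, but it is interpretable only if prior sprays do not track amount.

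The cost is three short order lists, one extra form field and some loss of scheduling freedom. No MEs are added. A reader might call this free; the documents do not cost the logistics, so low cost is the fair description. The change does not remove the average upward carry-over or the difference in reuse between site types. The recorded counts would at least allow both to be examined.
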